Participant protection and Zoom. Using the **Only authenticated** users can join setting will prevent guests who do not have an Ohio State Zoom account from entering the session. Since the meeting includes non-university participants, the PI will use the following strategies to control who can attend.

- ♣ Participants only with access can join
- Turn off the option to Join before Host
- ♣ Turn on the Waiting Room
- Meeting will be password protected

Participants will be encouraged to use their camera to facilitate interaction. However, participants will be a given the choice to turn off their camera and microphone and use the Zoom Chat if they prefer. Participants may use an avatar image of themselves in the Zoom room. Each cohort will chose a pseudonym for their cohort. Participants may share their contact information, not required, if they would like to support one another in their health goals. The study staff will not provide participants with each other's' contact information.

Field Notes

Research staff may describe their thoughts about factors they observed that contributed to the quality of each encounter by writing a brief field note. The field notes will be documented in REDCap. A descriptive qualitative analysis will be conducted to categorize themes.

IRB Approval date:

Version: 08/08/2023

10/05/2022

Intervention fidelity (Table 2) will be evaluated to provide assurance that MIM DASH and Caregiver Training are implemented as intended and will assure reproducibility of the protocol. The MIM DASH group will receive the Caregiver Training materials at the conclusion of the study.

Component	Data used to Evaluate Intervention Fidelity	Table 2. Intervention Fidelity		
Design	Detailed protocol manual for intervention sessions and common problem areas and weekly review of interventionist field notes.			
Training	Research Staff Training: Pre-study simulations and observed data collection. Data collection accuracy at start-up and maintenance			
	will be >.90. Interventionist Training: Each interventionist will complete training to competence under the supervision of PI [name] and			
	Co-l's [name], and [name]. All training will be video-recorded with feedback provided and corrected performance observed.			
Delivery	Delivery of Intervention: Field notes will be recorded for all sessions as evidence of completion and to document barriers and facilitators			
	to progress. Interventionist will complete key component check list following each session to provide documentation of participant			
	progress.			
Receipt	List of participant responses to each intervention session.			
Enactment	Weekly de-briefing of participants regarding performance of skills and strategies in "real-world" settings. Participant comments will be			
	recorded in interventionist session logs. Participant logs and diaries.			

Data Validity/Integrity It is the responsibility of the Principal Investigator to ensure that all team members handle data and related documentation appropriately. All participant information, including source documents must be reviewed by the PI and clinical team and entered into the REDCap database. There will be ongoing processing of data and quality checks by the study statistician and or PI.

Recruitment:

Participant recruitment will be tracked and reviewed in the research team meetings. In order to maintain confidentiality, the list, which includes the names of all potential participants, will be kept separately from the documentation and tracking spreadsheet in the College of Nursing R: Drive (duo authentication). Tracking will be carried out to determine which and how many individuals are interested in study participation, are eligible for study participation, enroll in the study, and complete the first assessments. Enrolled participants will be given code numbers and their study participation will continue to be tracked via spreadsheet in the College or Nursing R:Drive using and Excel spreadsheet. This will include documenting the occurrence and date of completion of data collection at each time point and their participation in the intervention.

Quality Assurance:

To minimize data-entry error and data-management miscoding, data will be entered into REDCap directly and we will have a paper forms as a back-up. If the data has to be transcribed into REDcap from a paper form, we will do a double data entry process. PI [name] and or designated study staff will review the data collected and all related documentation.

Data Storage:

Consent forms will be stored in REDCap. Participant lists (ID number and demographic information) will be stored in the College of Nursing R:Drive on a spread sheet. The PI and designated study staff will have access to data. All participant data collected via REDCap will be labeled only with a code number. These coded data will be kept separate from the master list that links participants to their consent forms. Only the PI and designated research study staff will have access to the data.

IRB Approval date:

Version: 08/08/2023

10/05/2022

This study will utilize REDCap (Research Electronic Data Capture), a software toolset and workflow methodology for electronic collection and management of clinical and research data, to collect and store data. The OSU Center for Clinical and Translational Science (CCTS) Research Informatics Services will be used as a central location for data processing and management. REDCap provides a secure, web-based application that provides an intuitive data manipulation interface, custom reporting capabilities, audit trail functionality, real-time data monitoring/querying of participant records, and variations of data exporting/importing. REDCap is hosted by OSUWMC IT in the Ackerman Datacenter ([name])

REDCap instance is located on internal OSUWMC network. Remote access to this network can be obtained over an encrypted VPN tunnel (AnyConnect) This VPN uses Protocol: DTLS and Cipher: RSA_AES_128_SHA1. Background checks are performed on all staff that are on the network or obtaining VPN access.

Termination for Significant Risk: Although the study is deemed low risk and adverse events are not anticipated, diligent monitoring will occur as specified above under Adverse Events Protocols. A participant that expresses concern about his or her participation or reports distress associated with receiving the intervention may be asked to discontinue participation in the study if there is concern about participant safety and wellbeing or about the safety and wellbeing of others. Likewise, if one of the research assistants, interventionists or supervising members of the Research Team expresses a concern about a participant's safety or wellbeing, the Office of Responsible Research Practices Adverse Events Reporting process will be used and it is possible that the participant could be asked to discontinue participation if there were concern about his or her, or others, safety and wellbeing.

Protection of Privacy. For all potential participants, the data collection interviews will take place in a private room with closed door. All research team members will be certified with The Ohio State University (OSU) IRB, HIPAA, and CITI training. Careful training and supervision of all study staff will ensure procedures are carried out in accordance with established protocols. Timely team meetings (at least twice monthly) will be conducted to evaluate consent procedures, study data collections, and other study activities to ensure consistency with planned study procedures. Should an adverse event occur, PI [name] will report this to the OSU IRB.

Protection of Confidentiality. Study staff will be carefully trained to protect participant confidentiality. They will work with participants to devise a plan for contacting them by phone, email, text messaging, or some other means determined by the participant, and decide whether or not messages may be left. Participants will be assigned a study identification number, and a master log will be created associating participant names and study number. The master log will be stored separately from data in the CON R: Drive folder. Only the PI and designated study staff will have access to the master log, and the master log will be destroyed at the end of the study. Study staff access to study data will be determined based on the relevance to their responsibilities. Only aggregate data will be reported for the dissemination of study findings.

Consents and any other forms with identifiable subject information will be maintained in a locked file separate from the filed study data which will be identified only by subject numbers. Data from questionnaires will be entered into REDCap. Destruction of paper logs and forms will follow OSU protocols. Findings will be reported in a manner in which individual data for specific participants are not identifiable.

To mitigate the risk that participants violate the privacy and confidentiality of others in their group sessions, we will ask that those participants (and their family/support person) refrain from discussing other participants outside the group. Likewise, they will be asked not to acknowledge having met if they encounter each other elsewhere. These steps are not foolproof, and participants will be informed of the associated risks at the time of consent.

IRB Approval date:

Version: 08/08/2023

10/05/2022

Protection against Physical Harm. The study poses minimal risks to the participants. All participants will receive the Blood Pressure Categories flyer from the American Heart Association and instructed to consult their provider if they have a systolic blood pressure higher than 180 mm Hg or diastolic blood pressure higher than 120 mm Hg. the participant would be instructed to seek immediate assistance or contact their provider. The designated research staff member will attend all sessions.

Protection against Psychological Harm. Survey questions are asked in a private setting and participants are reassured that they can refuse to answer any questions. To further promote participant comfort, frequent breaks will be taken during data collection. From our previous experience, participants are able to complete the study questionnaires without a sense of burden. To minimize emotional distress during the group sessions, interventionists and group leaders will be trained in observation for psychological or emotional discomfort as well as in how to deliver material in a supportive, nonjudgmental fashion. If the interventionists or group leader observes discomfort, then the designated study staff member and or interventionist will take the participant to a quiet area to provide support. The designated study staff member will also notify PI [name].

Advisory Board

We will rely on the Advisory Board to assist us with accessing the community by making introductions of study staff to key community leaders and members and identifying community assets (e.g., resources, organizations) to support the project. The Advisory Board will have a role in tailoring of the intervention and recommendations to promote sustainability of the project, dissemination, and problem-solving with the research team. The Community Advisory Board will meet bi-monthly via Zoom, more if needed. We will work closely with the Community Advisory Board to ensure that our de-identified summary of findings are fair and accurate and provide input on how best to disseminate the results back to the community. The Study PI is in charge of the meetings and no participant information will not be shared with the Advisory Board.

INTERNAL VALIDITY

The study is a RCT with equal attention for both conditions. We will repeat surveys measures over three time points (baseline, 1 month, 9 months) to reduce regression to the mean as an internal validity threat. We have also employed strategies to improve participant retention.

Retention. Participants will be enrolled for 9 months. We anticipate low drop out during this time. However, should a participant drop out for any reason (illness, refusal, etc.), then additional participants will be enrolled to maintain sample size. In studies longitudinal studies, a threat to internal validity is selection bias or selection threat. This can occur due to study drop out. To decrease the risk of participants dropping out of the study, we have employed several strategies.

- a. Data collection and intervention delivery option for weekends and evenings.
- b. Intervention delivery option for weekends and evenings.
- c. Reminder calls to participants for data collection and sessions.
- d. Participants will also receive a home blood pressure monitor and a MyPlate depicting a well-balanced diet of protein, fruit/vegetables, and carbohydrates.
- e. Free parking or round trip transportation is provided for data collection.
- f. With permission from the participant, we will send text messages, emails, and or phone call reminders for visits.
- g. Incentives include \$50 cash given to participants at each data collection point (baseline, 3 and 9 months).
- h. Data collectors will be available to go to the participant's preferred location if they do not want to come to the College of Nursing.

IRB Approval date:

Version: 08/08/2023

10/05/2022

Since participants may have a wait before baseline data are collected and the start of the group sessions, we have several incentives. We will send reminder greeting cards, postcards, and unexpected token gifts (each valued at under \$7, e.g., water bottle, cinch bag) to participants. In our experience, participants bond to such staff and remain in studies to a large degree because of the personal relationships and trust; a key component to working with the African American community. PI [name] has established community relationships with key stakeholders including the American Heart Association, Franklin County, Franklin County Hypertension Network, and local churches. If an increase in missed visits occurs, the PI and the project coordinator will review with the RAs the root cause for the missed visits and review procedures for contacting participants.

[name] will monitor any adverse events that arise in the course of the study. Any adverse events will be reported in writing to Ohio State University IRB. The PI will stop any data collection for the aim in which there has been an adverse effect until the adverse effect is resolved. A Safety Officer will be appointed to provide oversight of data collection and analyses. If the needs arise, a data safety and monitoring board will be formed. Given the low risks associated with lighting intervention (non-pharmacological education intervention), we do not foresee a need for a DSMB, but we will be working with a Safety Officer who can provide independent oversight of the project.

DATA ANALYSIS

Aim 1. Analysis. We will conduct descriptive data analyses to check data accuracy, summarize participant characteristics, and examine variable distributions. Data anomalies once identified will be fully investigated and remedial strategies will be considered as appropriate. We will use descriptive statistics to examine the feasibility and acceptability of the MIM DASH intervention and Caregiver Training, including a) approach-to-enrollment ratio; b) proportion of participants that complete all eight sessions of assigned intervention arm and attention control arm; c) frequency of completion of the follow-up calls or surveys; d) proportion of days the study protocol is fully adhered to and proportion of protocol deviation among interventionists; e) mean rating of MIM DASH intervention; and f) proportion of participants rating the MIM DASH intervention positively (4 or above). We will report point estimates along with 95% confidence intervals to indicate the precision of the estimates. Based on our experience enrolling African American participants in studies, feasibility will be defined by: a) enrolling at least 40% of potentially eligible patients and b) completion of at least 75% of the assigned intervention. Acceptability will be defined by an average rating of 4 and at least 80% participants rating the intervention positively.

Aim 2 Analysis. We will conduct intent-to treat analysis. Descriptive statistics including mean and standard deviation will be used to summarize each primary outcome and secondary outcome. We will also report mean differences, 95% confidences intervals, and effect sizes for both within- and between-group differences at each visit. The fixed effect of MIM DASH intervention will be examined by mixed effects models

Aim 3 Analysis. We will conduct mediation analysis for both groups. Each variable will be first summarized by descriptive statistics. Then we will examine the mediation effects of stress reactivity/stress resilience between the MIM DASH intervention or Caregiver Training and behavior change. The estimated mediation effects and 95% confidence intervals will be reported

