A small-scale two-group randomized controlled (RCT) pilot study of 28 African American female caregivers, age 40 and older with hypertension, will be conducted. We will determine the feasibility and acceptability of Mindfulness in Motion (MIM) plus the Dietary Approaches to Stop Hypertension (DASH). Participants will be randomized to either the MIM DASH intervention or the Alzheimer's Association Caregiver Training (attention control) delivered in 8 weekly, 1-hour group sessions via telehealth (video and telephone access). After completion of the intervention, both groups will receive eight weekly and then four monthly coaching calls or surveys through Mosio over the 9 months. To our knowledge, this is the first study that a) systematically employs one of the **Science of Behavioral Change key mechanisms underlying successful adoption** of health behaviors—stress reactivity/stress resilience and b) focuses solely on African American female caregivers of people living with dementia. The study aims are to:

AlM 1. Determine the feasibility and acceptability of MIM DASH and Caregiver Training for African American female caregivers with hypertension. Hypothesis: MIM DASH and Caregiver Training groups will be feasible and acceptable to caregivers. Method: We will track *feasibility*: screening to enrollment, attendance, attrition, completion of data collection procedures; and *acceptability*: treatment-specific preference ratings (prepost intervention). The Credibility Scale will capture attitudes towards the treatment condition and the participants' expectation of benefit once the treatment has been explained. Analysis: Feasibility and acceptability will be examined through descriptive statistics.

AIM 2. Explore the impact of MIM DASH as compared to Caregiving Training on caregiver stress and QOL. Hypothesis: MIM DASH group will have improved caregiver stress and QOL as compared to the Caregiver Training group. Method: The Perceived Stress Scale will be used as a measure of *caregiver stress* and the level of cortisol extracted from hair will be a proxy measure of *chronic stress*. The World Health Organization-5 will be used to measure QOL. The data will be collected in person and documented in REDCap at baseline, 3, and 9 months post-intervention. Analysis: We will conduct intent-to treat analysis and the fixed effect of MIM DASH intervention will be examined by mixed effects models.

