AIM 3. Investigate the potential mediation effects of stress reactivity/stress resilience between MIM DASH or Caregiver Training and self-care behaviors. Hypothesis: Higher stress reactivity will diminish the relationship while higher stress resilience will enhance the relationship between MIM DASH and the adoption of self-care behaviors. Method: Daily Inventory of Stressful Events and the Pittsburgh Stress Battery will be used to measure stress reactivity/stress resilience. Self-care behaviors will be measured using the Stress

IRB Approval date:

Version: 08/08/2023

10/05/2022

Management Practices survey and the Block Food Frequency Questionnaire for the DASH eating index (includes physical activity). The 4-Item Krousel-Wood Medication Adherence Scale will be used to measure medication adherence. The data will be collected in person and online survey at baseline, 3, and 9 months post intervention. Analysis: The mediation analysis will be employed to examine this pathway.

Impact. This pilot will make a substantive contribution to the science of behavior change by identifying basic mechanisms, in the adoption of healthy behaviors that can be used to implement self-care interventions to reduce health disparities in African Americans. **Findings from the pilot study will inform the infrastructure for a larger trial.**

BACKGROUND AND RATIONALE

African American women are disproportionately burdened with informal caregiving. In 2019, informal caregivers provided 18.6 billion hours of unpaid care to people living with Alzheimer's disease and related dementias (PLWD) with African American women providing 60% of this type of care. Although African American women generally endorse positive feelings about caregiving and express cultural justifications for providing care, they endure the adverse effects of chronic caregiver stress—increased cortisol and HTN. Indeed, HTN is the leading cause of cardiovascular disease (CVD) among African American women affecting 56.7%. Yet, to our knowledge no behavioral intervention studies have addressed the dynamic interplay of chronic caregiving stress and HTN self-care in African American women. Our intervention, study thus addressees a significant gap.

Current caregiver interventions are not as effective for African Americans as compared to other

"Caring for myself is not self-indulgence, it is self-preservation, and that is an act of political warfare." ~Audre Lorde

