 31 African Americans in 30 days Zero drop out 90% attended 100% of sessions 	 Identified facilitators to HTN self-care Group support Access to health professional Family support Identified barriers to HTN self-care Interpersonal communication stress Complex diet regimens 	 True control group 50% attrition rate Clinically significant reduction in systolic BP in the MIM DASH group (-7.2mm Hg) relative to the attention only group (-7.) Intervention fit within routine and culture

findings demonstrate our ability to recruit, retain, and deliver health behavior interventions to African Americans. Our interprofessional team is well-poised to conduct this intervention study given our preliminary work that can be transferrable to hypertensive African American women caring for PLWD. The primary investigator has over 6 years' experience conducting culturally informed research in this population.

We incorporated the Information-Motivation-Behavioral Skills model in our conceptual framework to promote health behavior change. The antecedents are biologic characteristics that may influence outcomes. The intervention has three components: knowledge of basic information regarding an illness/disease (HTN), motivation though learning in a socially supportive environment, and behavioral skills to manage stress and HTN. The Science of Behavior Change indicates stress reactivity/stress resilience affects behavior change. Through implementation of Mindfulness in Motion to affect stress reactivity and promote stress resilience, we can change the body's response to stress and influence the adoption of DASH self-care behaviors, lowering caregiver stress and improving QOL.

STUDY PROCEDURES

RESEARCH DESIGN

Randomized-controlled trial.

SAMPLE

Sample. A sample of 28 African American women (age 40 and older) with a diagnosis of hypertension, who are caregivers of persons living with dementia (PLWD).

IRB Approval date:

Version: 08/08/2023

10/05/2022

Setting. In an effort to facilitate trust with potential participants, we intend to hire research staff who are ethnically similar to the participants. PI [name] and co-I [name] are both African American researchers and will assist study staff to explain study aims and protocols to the key stakeholders in the community. The study will take place in via telehealth with data collection occurring in-person.

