Hair cortisol (HC) will be used as a proxy for chronic stress. To collect the hair samples, approximately 25-75 mg of hair (approximate width of shoelace tip when bunched) will be cut from the posterior vertex region of the scalp as close to the scalp as possible. The posterior vertex has the lowest variation in cortisol levels, and is the preferred area for sampling. Participants will be surveyed on corticosteroid use as these medications may suppress cortisol levels, and on their hair care practices, such as frequency of washing, chemical treatments and hair product use. To prep for assay, the hair sample is cut, then washed twice with isopropanol and dried over 1 to 3 days. A total of 10-75 mg of hair is placed into a microcentrifuge tube, minced, and then ground in Retsch 400 Mill. A total of 1.1 ml of HPLC-grade methanol is added to the ground sample, and incubated for 18-24 hours at room temperature with constant agitation. The tubes are centrifuged at 5000g for 5 min at room temperature to pellet the powdered hair. The entire amount (~1 ml) of supernatant is transferred to a clean microcentrifuge tube and the methanol is removed by evaporation using a stream of air for 6-8 hours at room temperature. The cortisol extract is reconstituted in 100ul of Salimetric immunoassay cortisol analysis diluent buffer. Samples are assayed in duplicate and inter- and intra-assay coefficients of variation calculated. HC levels are expressed in hair as pg/mg and generally logged due to skewed distributions as needed. Hair samples will be collected at baseline and 9 months.

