trials of basic arithmetic problems lasting one minute per trial. Participants who scores 60% or greater, will advance to the Random-Medium level; those who do not will repeat Easy. Prior to the 3rd trial, the data collector will place the BP cuff on the participants left arm unless contraindicated. At the 30-second mark of the 3rd math trial, the data collector will use an automatic BP machine (clinician grade) to measure systolic BP, diastolic BP and heart rate. Significant Other Collaborator, [name] is a neuropsychologist and will assist with training data collectors to administer the test and interpretation of data. Survey to Evaluate the Pittburgh Stress Battery is a one-question Likert scale to evaluate how challenging the participants found the PBS to be. Selfcare behaviors are measured using Stress Management Practices survey part A, a list of 13 statements such as "I am able to use muscle relaxation techniques to reduce any tension I experience" that is measured on a Likert scale. Scores range from 0 to 52 with higher scores indicating greater use of stress management strategies. Block Food Frequency Questionnaire (includes physical activity) is a validated measure with a food and beverage list that includes 127 items, plus supplementary questions to allow for the adjustment of fat, protein, carbohydrate, sugar, and whole grain content. The questionnaire ascertains the frequency with which each food or beverage was usually consumed, and offers nine continuous responses ranging from "never" to every day" for most foods. The DASH Index that is calculated using data from the Block Food Frequency Questionnaire uses a quintile system to score foods related to the DASH diet. All of the components are equally weighted. Intake of vegetables, fruits (including fruit juice), nuts and legumes, whole grains were scored from 1 (lowest quintile) to 5 (highest quintile). The overall DASH component scores range from 8 to 40. The 4-Item Krousel-Wood Medication Adherence Scale captures four domains of adherence behavior. 78 Scores range from 0 to 4 with a score of 1 or greater indicating lower adherence. These data will be collected at baseline, 3 and 9 months. To reduce participant burden, the Block Food Frequency Questionnaire data will be collected at baseline and 9 months.

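### The aims promise 3-month hair cortisol and DASH Index values that the schedule does not collect, and Aim 3 names no visits for mediator and outcome

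*Combined protocol and SAP*

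**What the plan says.** **Aims.** Aim 2 in the Introduction names the Perceived Stress Scale, hair cortisol and the WHO-5, and then says "The data will be collected in person and documented in REDCap at baseline, 3, and 9 months post-intervention". Aim 3 names the Daily Inventory of Stressful Events and the Pittsburgh Stress Battery as mediators. Its self-care measures are stress management practices, the Block questionnaire with the DASH Index, and medication adherence. Of all of these it says "The data will be collected in person and online survey at baseline, 3, and 9 months post intervention".

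**Schedule.** Under Measurement/Instrumentation, the opening paragraph refers to Table 1 for timing. Table 1 has no 3-month mark for the Block questionnaire, the DASH Index or hair cortisol. The text confirms this for hair ("Hair samples will be collected at baseline and 9 months") and for diet ("the Block Food Frequency Questionnaire data will be collected at baseline and 9 months"), where the stated reason is participant burden.

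**Analysis.** The Aim 2 Analysis promises mean differences, confidence intervals and "effect sizes for both within- and between-group differences at each visit". The Aim 3 Analysis says "Then we will examine the mediation effects of stress reactivity/stress resilience between the MIM DASH intervention or Caregiver Training and behavior change". It names no visit for either variable and no baseline adjustment.

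**Framework.** Preliminary Work gives the direction of effect: through mindfulness, "we can change the body's response to stress and influence the adoption of DASH self-care behaviors".

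**The concern.** There are two linked problems.

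The first is a contradiction about which data will exist. Read with the Aim 2 Analysis, the aims commit the study to a 3-month hair cortisol comparison for which no sample is taken. They also suggest a 3-month diet outcome that Aim 3 will not have.

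The second has more consequence. A mediation claim needs the mediator to come before the outcome. The DASH Index has a single follow-up value, at 9 months, and the mediators are measured at 3 and 9 months. If the analyst pairs 9 months with 9 months, an association that arises because better self-care lowers stress would be reported in the same form as one that runs from stress to self-care. Aim 3 is presented as a study of mechanism, and the findings are meant to lead to a larger trial. With the visits unspecified, the pairing could also be chosen after the results are known.

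**Working it through.** The plan gives no figure to reproduce on this point. The check compares the schedules and lists the possible visit pairs.

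**1. Scheduled values, N = 28 (Sample)**
- Implied by the aims: 28 × 3 visits = 84 values per measure.
- Scheduled for hair cortisol and for the DASH Index: 28 × 2 visits = 56 each.
- Difference: 28 values per measure, all at 3 months. Each measure has one follow-up comparison, at 9 months.
- Perceived Stress Scale, WHO-5, stress management, medication adherence, Daily Inventory and stress battery: marked at all three visits, so 84 each and no conflict.

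The blank 3-month cells are not a fault of text extraction, because the hair and diet paragraphs say the same in words.

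**2. Post-baseline pairs (mediator visit, outcome visit)**
- DASH Index: (3, 9) and (9, 9).
- Stress management and medication adherence: (3, 3), (3, 9), (9, 3) and (9, 9).
- In each case only (3, 9) puts the mediator first.

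**3. Does the visit window upset the order?** Measurement/Instrumentation allows data collection within 8 weeks of the planned date. Take a month as 52/12 weeks, count both visits from the same starting point, and read the window as running either way:
- 3-month visit: 13 ± 8, so weeks 5 to 21.
- 9-month visit: 39 ± 8, so weeks 31 to 47.
- Smallest gap: 31 − 21 = 10 weeks.

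The order survives. The gap does not depend on whether the clock starts at baseline or later, provided both visits use the same clock.

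**4. What the instruments cover.** The Daily Inventory asks about the past 24 hours. The Block questionnaire asks about usual consumption. In a (9, 9) pairing the diet outcome therefore largely describes a time before the stress report, which is the reverse of the framework's order.

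**The case against.** **The schedule conflict is loose summary wording.** Each aim has one generic timing sentence for several instruments, the measurement section defers to Table 1, and the omission of diet at 3 months is deliberate and explained. Staff following Table 1 would not be misled. The phrase about every visit can also be read as every visit at which the measure is taken. This largely stands, and it makes the first part a correction of text.

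**The plan does not choose the wrong pairing.** A reader might infer that Aim 3 does not use the ordered pairing. The documents do not support that: they are silent on the visits, and nothing excludes 3 months to 9 months. The defect is the missing specification.

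**The loss at 3 months is narrow.** A reader might also infer that 3-month comparisons are lost generally. They are not. The promise for every visit sits under Aim 2, so it fails for hair cortisol only. No by-visit DASH Index comparison is promised under Aim 3.

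**The ordered pairing is not a cure.** Mindfulness and diet teaching are delivered in the same eight sessions, so diet may already have changed by 3 months, and there is no 3-month DASH Index to adjust for. A 24-hour stress report is a weak predictor of diet about six months later. Both points stand. The lagged analysis reduces the problem of reverse order but does not remove it.

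**This is an exploratory pilot of 28 women.** Aim 3 speaks of potential mediation, and the interval around any indirect effect will be wide. That limits the severity. It does not justify leaving the pairing open, because in a small sample the choice of pairing can change the result more.

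**Conclusion.** The point holds in two limited parts.

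First, the aims contradict Table 1 and the measurement text for hair cortisol and the DASH Index: 56 scheduled values each, against 84 implied. One promised comparison, hair cortisol at 3 months, cannot be produced, and Aim 3 has no 3-month diet outcome. The 9-month comparisons are unaffected.

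Second, the Aim 3 analysis leaves the mediator and outcome visits open. This permits a same-visit 9-month analysis that cannot support an order in which the stress response changes first and behaviour follows. The ordered pairing is available from data already scheduled, at least 10 weeks apart under the stated window assumptions.

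A reader might want a size for the false indirect effect that a same-visit analysis could show. The documents give neither an arm effect on the mediators nor a correlation between mediator and outcome, so any figure would rest entirely on assumed inputs. None is offered. The change should be made, but its weight is moderate for a study whose first aim is feasibility.

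**What to change.** **Schedule.** Amend the timing in Aims 2 and 3 so that hair cortisol and the Block questionnaire/DASH Index read baseline and 9 months. Make the same exception in the Measurement/Instrumentation paragraph that first describes hair cortisol and closes with a three-visit statement. Limit the between-group estimates for both measures to 9 months. Reconcile the Internal Validity section at the same time, because it gives a third schedule with a 1-month visit.

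**Mediation.** In Aim 3 and the Aim 3 Analysis, make the main analysis use the 3-month Daily Inventory and stress-battery values as mediator and the 9-month self-care measures as outcome, adjusted for the baseline mediator and the baseline outcome. Label any analysis that pairs 9 months with 9 months as cross-sectional association.

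**Limits to state in the plan.** The lagged effect may be smaller than a same-visit one. The 24-hour report is a weak predictor of later diet. Diet may have changed before 3 months without being measured. Confounding of mediator and outcome remains.

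**Cost.** Wording only. No visit, sample or questionnaire is added.
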